# 6.8.2 Determination of end of clinical trial (all patients)

The clinical trial will end 30 days after the last IMP administration.

### 6.9 INTERIM ANALYSIS

An interim analysis is planned after the first 17 patients of the Expansion Part. Refer to Section 13.5 for details on interim analysis.

### 6.10 STUDY COMMITTEES

The Study Committee will include the Principal Investigator or delegate at each site, clinical team members from the Sponsor, and independent ad hoc experts, when appropriate. The Study Committee will review clinical data, including SAEs, adverse events of special interest (AESIs), DLTs, and deaths, on a regular basis. The Study Committee will decide whether or not to escalate to the next dose level based on their knowledge of the whole safety profile and on the design of the study. The Study Committee will also make recommendations on the choice of the RP2D. Decisions regarding patient treatment and cohort expansion will be discussed and will be clearly documented in the discussion minutes.

# 7 SELECTION OF PATIENTS

#### 7.1 NUMBER OF PATIENTS

It is anticipated that approximately 72 patients (67 to 77 patients) will be enrolled in this study: 30 to 40 patients in the Dose Escalation Part and 37 patients in the Expansion Part (Section 13.1).

### 7.2 INCLUSION CRITERIA

- I 01. Confirmed diagnosis of primary or secondary AML (any subtype except acute promyelocytic leukemia) according to World Health Organization (WHO) classification or MDS with a Revised International Prognostic Scoring System (R-IPSS) risk category of intermediate or higher (36) (Appendix E). Patients must have exhausted available treatment options and must not be eligible for any treatment known to provide clinical benefit.
- I 02. Patients with AML must have relapsed or refractory disease that has been resistant to available therapies, as defined by any 1 of the following criteria:
  - Leukemia refractory to  $\geq 2$  intensive remission induction attempts,
  - Leukemia in first relapse within 1 year following allogeneic stem cell transplant,
  - Leukemia in second or higher relapse,
  - Not eligible for intensive remission induction therapy and have persistent leukemia despite ≥2 cycles of therapy, including any of the following: hypomethylating agent (eg, decitabine or 5-azacitidine), chemotherapy, or targeted agents (eg, gemtuzumab ozogamicin or enasidenib).
- I 03. During the Dose Escalation Part, patients with B-ALL without extramedullary lesions, in second or subsequent relapse, could also be recruited at any DL ≥3 during the 3 +3 escalation period. B-ALL patients should have completed previously ≥1 cycle of a salvage regimen, including any of the following: chemotherapy, blinatumomab, tyrosine kinase inhibitors, cellular therapy (eg, tisagenlecleucel), or targeted agents (eg, inotuzumab ozogamicin). Patients must have exhausted available treatment options and must not be eligible for any treatment known to provide clinical benefit.
- I 04. Patients with HR-MDS must have >10% blasts in the bone marrow at the time of enrollment and fit one of the following categories:
  - Not eligible for induction therapy and having completed ≥2 cycles of therapy, including any of the following: hypomethylating agent (eg, 5-azacitidine or decitabine), chemotherapy, or targeted agents.
  - Not eligible for allogeneic stem cell transplant and having completed ≥1 course of induction therapy.

I 05. Signed written informed consent.

### 7.3 EXCLUSION CRITERIA

Patients who have met the above inclusion criteria listed in Section 7.2 for one of R/R AML, B-ALL, or HR-MDS, will be screened for the following exclusion criteria:

- E 01. Age <16 years old.
- E 02. Eastern Cooperative Oncology Group (ECOG) performance status >2 (11).
- E 03. Abnormal laboratory parameters, including the following:
  - Total bilirubin >1.5 x ULN unless Gilbert's syndrome is present,
  - ALT, AST, or alkaline phosphatase >2.5 x ULN,
  - Serum creatinine >2 x ULN and/or creatinine clearance <30 mL/min,
  - Grade 4 hematological toxicity: febrile neutropenia, bone marrow hypocellularity, symptomatic disseminated intravascular coagulation, life-threatening anemia, or life-threatening thrombotic thrombocytopenic purpura,
  - White blood cell count  $> 30,000/\text{mm}^3$ .
    - If the white blood count exceeds 30,000/mm^3, hydroxyurea may be used to reduce the white blood cell count to < 30,000/ mm^3 at start of treatment.
    - Hydroxyurea may be administered to patients at the Investigator's discretion during Cycle 1, but must be stopped ≥1 day prior to Cycle 2, Day 1.
- E 04. Graft-versus-host disease following allogeneic stem cell transplantation requiring treatment with more than 10 mg of oral prednisone or equivalent daily. The stem cell transplant and/or donor lymphocyte infusion should have been performed more than 3 months before study treatment start.
- E 05. History of an active or chronic autoimmune condition that has required or requires therapy.
- E 06. Prior treatment with an anti-CD123-directed agent.
- E 07. Second primary malignancy that requires active therapy. Adjuvant hormonal therapy is allowed.
- E 08. Previous treatment with chemotherapy, radiotherapy, or immunotherapeutic agents in the 4 weeks prior to IMP administration (Cycle 1 Day 1), except for hydroxyurea.
- E 09. Previous treatment with any other investigational agent in the 4 weeks prior to IMP administration (Cycle 1 Day 1).

- E 10. Receiving at the time of first IMP administration concurrent steroids >10 mg/day of oral prednisone or the equivalent for ≥3 months, except steroid inhaler, nasal spray, or ophthalmic solution.
- E 11. Requirement for tocilizumab for any other diagnosis within ≤14 days before the first administration of SAR440234.
- E 12. Known contraindication to any of the noninvestigational medicinal products (NIMPs) (dexamethasone and tocilizumab), acetaminophen, diphenhydramine, ranitidine, montelukast or similar agents.
- E 13. Evidence of active central nervous system leukemia at the time of enrollment.
- E 14. Known acquired immunodeficiency syndrome (AIDS-related illnesses) or HIV disease requiring antiretroviral treatment, or having active hepatitis A, B or C infection, or tuberculosis.
- E 15. Pregnant and breast-feeding women, female patients of childbearing potential, and male patients with female partners of childbearing potential who are not willing to avoid pregnancy by using an adequate method of contraception (2 barrier method or 1 barrier method with a spermicide, intrauterine device, or hormonal contraception with inhibition of ovulation, for 2 weeks prior to the first dose of SAR440234, during treatment, and 12 weeks after the last dose of study treatment). A woman is considered of childbearing potential, ie, fertile, following menarche and until becoming postmenopausal unless permanently sterile.
- E 16. Any country-related specific regulation that would prevent the patient from entering the study.
- E 17. Any clinically significant, uncontrolled medical conditions that, in the Investigator's opinion, would expose excessive risk to the patient or may interfere with compliance or interpretation of the study results.
- E 18. Patients weighing <60 kg (DL1, DL2, and DL3 only).

Patients who have been withdrawn from the study after the study treatment has started cannot be reincluded in the study. Their inclusion and treatment number must not be re-used.

Rescreening is permitted for patients who have not received treatment in this study.

# 8 STUDY TREATMENTS

#### 8.1 INVESTIGATIONAL MEDICINAL PRODUCT

The IMP is presented as a lyophilisate powder for solution for IV injection at (CD3-CD123)

# 8.1.1 Dose of drug per administration

Starting dose of SAR440234 is described in Section 6.2.

# 8.1.2 Preparation, reconstitution, and administration of SAR440234

Dilution method, calculation of volume to be infused, and administration of SAR440234 are detailed in the Pharmacy Manual.

SAR440234 requires a grant property and the pharmacy Manual. Special care should be taken to avoid accidental overdose with the medication.

Infusion-related reactions are expected, thus infusion rates should be gradually increased every 30 minutes, as tolerated, for each administration. Minimum and maximum infusion rates have also been defined for each dose level, as described in the Pharmacy Manual.

The infusion rate schedule for SAR440234 is described in the Pharmacy Manual.

# 8.2 NONINVESTIGATIONAL MEDICINAL PRODUCT(S)

**Dexamethasone:** 4 mg/mL for IV injection.

**Tocilizumab:** 200 mg/10 mL vial for IV injection.

**Montelukast:** 10 mg tablet for oral administration.

Dexamethasone 20 mg IV will be instituted as systematic premedication 4 hours and 1 hour prior to each initial IMP administration.

Montelukast tablets 10 mg will be given orally once, 4 hours before the start of SAR440234 infusion.

Dexamethasone 20 mg IV must be repeated 5 hours after the start of infusion if CRS Grade 2 has occurred in a previous patient or previous administration in the same patient. This rule will be applied for the same patient who experiences a CRS event for subsequent infusions and for all patients subsequently enrolled at that dose level or higher.

29-Aug-2019 Version number: 2

For each patient treated, the clinical site must have at least 2 full doses of tocilizumab in the clinical pharmacy ready for immediate administration in case of CRS Grade 2 or above. Guidelines for management of patients with CRS are included in Section 6.7.

For patients with Grade 2 CRS, tocilizumab will be administered at 8 mg/kg infused over 1 hour for patients weighing ≥30 kg (maximum dose 800 mg) or 12 mg/kg infused over 1 hour for patients weighing <30 kg.

If there is insufficient improvement in CRS within 12 hours, tocilizumab may be repeated at the same dose every 12 hours for a total of 3 doses. The interval between consecutive doses should be at least 8 hours. Subcutaneous infusion of tocilizumab is not approved for CRS treatment. Tocilizumab must not be used for prophylaxis of CRS. Patients with Grade 3 or Grade 4 CRS should be treated with tocilizumab as for patients with Grade 2 CRS. For patients with Grade 3 or Grade 4 CRS who do not respond to tocilizumab within 24 hours, dexamethasone 10 mg IV should be given every 6 hours.

For patients weighing ≥30 kg or more, tocilizumab should be diluted in 100 mL of 0.9% or 0.45% sodium chloride injection USP for IV infusion and administered by drip infusion over 1 hour. For patients weighing <30 kg, tocilizumab should be diluted in 50 mL of 0.9% or 0.45% sodium chloride USP for IV infusion and administered by drip infusion over 1 hour. Tocilizumab should not be given as a bolus or push.

#### 8.3 INVESTIGATIONAL MEDICINAL PRODUCT PACKAGING AND LABELING

SAR440234 will be supplied in boxes of

Packaging is described in the Pharmacy Manual.

The content of the labeling is in accordance with the local regulatory specifications and requirements.

#### 8.4 STORAGE CONDITIONS AND SHELF LIFE

Investigators or other authorized persons (eg, pharmacists) are responsible for storing the IMP/NIMP in a secure and safe place in accordance with local regulations, labeling specifications, policies, and procedures.

Control of IMP storage conditions, especially control of temperature (eg, refrigerated storage), and information on in-use stability and instructions for handling the sanofi compound must be managed according to the rules provided by the Sponsor.

SAR440234 must be stored at until use. All vials must be kept in their box until use.

Details of the storage conditions for the diluted solution are provided in the Pharmacy Manual.

#### 8.5 RESPONSIBILITIES

The Investigator, the hospital pharmacist, or other personnel allowed to store and dispense the IMP will be responsible for ensuring that the IMP used in the clinical trial is securely maintained as specified by the Sponsor and in accordance with applicable regulatory requirements.

The IMP will be dispensed in accordance with the Investigator's prescription, and it is the Investigator's responsibility to ensure that an accurate record of IMP issued and returned is maintained.

Any quality issue noticed with the receipt or use of an IMP; deficiency in condition, appearance, pertaining documentation, labeling, expiration date, etc) must be promptly notified to the Sponsor. Some deficiencies may be recorded through a complaint procedure (see Section 10.5.7).

A potential defect in the quality of IMP may be subject to initiation of a recall procedure by the Sponsor. In this case, the Investigator will be responsible for promptly addressing any request made by the Sponsor, in order to recall IMP and eliminate potential hazards.

Under no circumstances will the Investigator supply IMP to a third party, allow the IMP to be used other than as directed by this clinical trial protocol, or dispose of IMP in any other manner.

# 8.5.1 Treatment accountability and compliance

Administration of the IMP will be supervised by the Investigator or Subinvestigator.

The person responsible for drug dispensing is required to maintain adequate records of the IMP. These records (eg, drug movement form) include the date the IMP is received from the Sponsor, dispensed for patient, and destroyed or returned to the Sponsor. The packaging batch number (PR Nr) on the vial must be recorded on the drug accountability form.

The person responsible for drug administration to the patient will record precisely the date, infusion rate, and start and stop times of the drug administration to the patient.

#### 8.5.2 Return and/or destruction of treatments

All used and partially used IMP (SAR440234) will be destroyed at the study site after an accurate accountability has been performed and signed by the Investigator (or the pharmacist).

All unused IMP may be destroyed at the site or retrieved by the Sponsor. The Investigator will not destroy the unused IMP unless the Sponsor provides written authorization.

A detailed treatment log form of the destroyed and/or returned IMP will be established with the Investigator (or the pharmacist) and countersigned by the Investigator and the Monitoring Team.

#### 8.6 CONCOMITANT TREATMENT

All treatments being taken by the patient 14 days prior to registration onto the study, or at any time during the study in addition to the IMP are regarded as concomitant treatments, and the type, dose and route of administration must be documented on the appropriate pages of the eCRF. Hydroxyurea may be administered to patients at the Investigator's discretion during cycle 1 but must be stopped ≥1 day prior to the start of cycle 2.

Concomitant medications should be kept to a minimum during the study. However, if these are considered necessary for the patient's welfare and are unlikely to interfere with the IMP, they may be given at the discretion of the Investigator and recorded in the eCRF:

• Supportive treatment as medically indicated for the patient's wellbeing may be prescribed at the Investigator's discretion. Every medication or treatment taken by the patient during the trial and the reason for its administration must be recorded on the eCRF.

Details of specific treatments for the management of AEs are provided in Section 6.7.

The following concomitant treatments are not permitted during this study:

- Concurrent treatment with other investigational drugs.
- Concurrent treatment with any other anticancer therapy not specified in the protocol, including immunotherapy, hormonal therapy, targeted therapy or biological therapies.
- Radiotherapy, even if palliative in intent, may not be given during the study.
- Prophylactic use of hematopoietic growth factors (eg, G-CSF, GM-CSF, erythropoietin) during the DLT observation period in the Dose Escalation Part only.
- Cytokine release may modulate CYP450 enzymes (decrease activity) and cause drug-drug interactions by increasing concentrations of drugs primarily metabolized by CYPs.
   Therefore, patients treated or intended to be treated with drugs known to be CYP substrates with a narrow therapeutic index (Appendix B) should be carefully monitored for toxicity. Cytokine release may also have an impact on transporters. Therefore, patients should be monitored closely when treated, or intended to be treated, with transporter substrates that have a narrow therapeutic index. These drugs include: digoxin, glyburide, and methotrexate.

# 8.7 POST INVESTIGATIONAL MEDICINAL PRODUCT

The patient's treatment plan after discontinuation of the IMP will be at the discretion of the treating physician.

# 9 ASSESSMENT OF INVESTIGATIONAL MEDICINAL PRODUCT

#### 9.1 SAFETY

The major purpose of this Phase 1/2A study is to establish, based on DLTs, the MTD of SAR440234 administered IV weekly (except for Cycle 1 Week 1 in DL ≥3 when 2 administrations will be given) to patients with hematologic malignancy (R/R AML, B-ALL, or HR-MDS). Safety is thus the primary study endpoint and will be assessed continuously.

The safety profile will be assessed from the findings of physical examinations (preferably by the same physician in each center), laboratory tests, and reports of AEs, etc, and will be based on incidence, severity (as graded by the NCI-CTCAE v4.03; except for CRS, which will be graded according to the 2014 NCI Consensus Guidelines, Table 10), and cumulative nature of TEAEs (defined as AEs that develop or worsen in grade or become serious during the on-treatment period).

# 9.1.1 Dose-limiting toxicities

With an objective of defining the RP2D and dose schedule, the safety of SAR440234 will be evaluated using the following assessments during the Dose Escalation Part:

- Incidence of DLT (as defined in Section 6.2.1) observed during the DLT observation period (6 IMP administrations).
- Incidence of allergic reactions/hypersensitivity and CRS/acute infusion reactions.

Potential and IMP-related DLTs will be considered as AESIs. As such, the Investigators will be required to report them to the Sponsor within 24 hours of the Investigator becoming aware of each event. The Investigator will attach the DLT-specific CRF page to the transmitted DLT/AESI form or will complete the specific DLT form in the electronic case report form (eCRF).

Potential DLTs are defined as the occurrence of any of the following related to the study therapy using NCI-CTCAE v4.03, or the NCI Consensus Guidelines for grading CRS (Table 10), as appropriate:

#### Hematological abnormalities:

- Grade 4 hematological toxicities, ie, new onset or worsening of life-threatening hematological abnormalities after administration of SAR440234:
  - Grade 4 bone marrow hypocellularity, if not caused by disease progression and not improved to baseline value or Grade ≤1 within 14 days,
  - Grade 4 decreased neutrophils, if not present at baseline and not resolved to baseline value or Grade ≤1 within 14 days,
  - Grade 4 febrile neutropenia not resolved within 7 days,

- Grade 4 decreased platelet count, if not present at baseline and not improved to baseline value or Grade ≤1 within 14 days,
- Grade 4 anemia, if not improved to baseline value or Grade ≤1 within 14 days.

# Nonhematological abnormalities:

- Any Grade ≥3 nonhematological AE unless either caused by disease progression or obviously unrelated cause or caused by a laboratory abnormality without associated clinical consequences that resolves within 5 days.
- Any TEAE that, in the opinion of the Principal Investigator and Sponsor, is of potential clinical significance such that further dose escalation would expose patients to unacceptable risk.
- Grade 3 or Grade 4 CRS.
- Grade 2 CRS if it persists for >48 hours or is present <48 hours before the time when the next planned dose of SAR440234 is due.

**Other:** IMP-related adverse reaction leading to a delay or omission of more than 2 weeks between 2 planned administrations of SAR440234 due to failure to improve to baseline or Grade  $\leq 1$ .

At the end of each appropriate cycle (ie, end of Cycle 1), each patient must be assessed by the Investigator as to whether or not the patient experienced a DLT. This information must be recorded on the appropriate eCRFs, and an electronic DLT notification (either DLT or not) will be sent to the Sponsor, before a subsequent cycle may begin.

The reported potential DLTs will be reviewed by the study committee in order to determine their relationship to the IMP.

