# 6.2.1 Starting dose and dose levels

SAR440234 will be administered IV on Day 1, Day 4 (DL≥3), Day 8, and weekly thereafter in Cycle 1 for a 42-day cycle. The dosing regimen will be weight-based; however, if a patient weighs >140 kg, the patient's weight will be capped at 140 kg for dose calculations. The administration of the investigational medicinal product (IMP) will begin at the selected safe starting dose for an FIH trial, based on the MABEL, and by integration of all available in vivo and in vitro data at the start of the study.

A 3+3 dose escalation scheme will be used, based on DLTs observed during the first 42 days following the first administration of IMP in the first cycle (the DLT observation period). The goal is to treat 3patients per dose level in order to follow a 3+3 design. In this FIH study, potential DLTs are defined as the following:

• Any Grade ≥3 nonhematological AE, unless either caused by disease progression or an obviously unrelated cause or caused by a laboratory abnormality without associated clinical consequences that resolves within 5 days (AE's related to cytopenias that were present prior to starting SAR440234 or to underlying leukemia will not be considered DLT's).

- Grade 4 hematological toxicities as defined in NCI-CTCAE v4.03, ie, new onset or
  worsening of life-threatening hematological abnormalities after administration of
  SAR440234 (AE's related to cytopenias that were present prior to starting SAR440234 or
  to underlying leukemia will not be considered DLT's).
  - Grade 4 bone marrow hypocellularity, if not caused by disease progression and not improved to baseline value or Grade ≤1 within 14 days,
  - Grade 4 decreased neutrophils, if not present at baseline and not resolved to baseline value or Grade ≤1 within 14 days,
  - Grade 4 febrile neutropenia not resolved within 7 days,
  - Grade 4 decreased platelet count, if not present at baseline and not improved to baseline value or Grade ≤1 within 14 days,
  - Grade 4 anemia, if not improved to baseline value or Grade ≤1 within 14 days.
- Grade 3 or Grade 4 CRS.
- Grade 2 CRS if it persists for >48 hours or is present <48 hours before the time when the next planned dose of SAR440234 is due.
- Any treatment-emergent adverse event (TEAE) that, in the opinion of the Principal Investigator and Sponsor, is of potential clinical significance such that further dose escalation would expose patients to unacceptable risk.

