- IMP-related adverse reaction (unless caused by disease progression or an obviously unrelated cause) lasting more than 2 weeks with failure to recover to baseline or improve to Grade <1.

During the Dose Escalation Part, escalation to the next dose level cohort will occur after the last patient has completed the DLT observation period for the previous dose level. Within a dose level, subsequent patients will initiate treatment at least 1 week after the first patient in that dose level started treatment with SAR440234.

The occurrence of DLTs will inform the dose recommendation that will be used during the Expansion Part.

Response will be evaluated by a bone marrow aspirate at the end of Cycle 1 (Day 42 ±2 days). Patients may continue treatment with the IMP as long as clinical benefit is possible, or until disease progression, unacceptable adverse reaction, patient's decision to stop the treatment, or other reason for discontinuation (Section 6.5). Bone marrow aspirate will be performed on Day 42 (±2 days) of Cycle 2. Additional bone marrow aspirate is required if onset of cytopenia >14 days before or after Day 42. Subsequent bone marrow aspirates will be performed when clinically indicated, as determined by the treating physician. Additional bone marrow aspirate shall be performed as clinically indicated or if any of the following occurs: if decreased neutrophil count Grade 4, decreased platelet count Grade 4, febrile neutropenia Grade 3 and Grade 4, or anemia Grade 4 occurs with onset in >14 days before or after Day 42.

Response assessment will be performed according to the International Working Group (IWG) 2003 recommendations for AML (19) and the revised 2000 criteria for HR-MDS (34), and the 2016 National Comprehensive Cancer Network (NCCN) Guidelines for ALL (Appendix D, Appendix F, and Appendix H).

If at the end of a cycle the patient exhibits clinical benefit by symptoms or response criteria and does not meet study treatment discontinuation criteria, the patient may continue therapy until an unacceptable AE, disease progression, patient's decision to stop the treatment, or any other reason.

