# 10.5.5 Adverse event of special interest

An AESI is an AE (serious or nonserious) of scientific and medical concern specific to the SAR440234 program, for which ongoing monitoring and immediate notification by the Investigator to the Sponsor is required. Such events may require further investigation in order to characterize and understand them. Adverse events of special interest may be added, modified or removed during a study by protocol amendment.

Investigational medicinal product related DLTs (as defined in Section 9.1.1) are considered as AESIs, and as such, the Investigators will be required to report them to the Sponsor within 24 hours of the Investigator becoming aware of the event. The Investigator will attach the DLT-specific eCRF page to the DLT/AESI form.

Additional AESIs include the following:

- Pregnancy of a female patient entered in a study as well as pregnancy occurring in a female partner of a male patient entered in a study with IMP/NIMP:
  - Pregnancy in a female patient or in a female partner of a male patient will qualify as an SAE only if it fulfills one of the seriousness criteria (see Section 10.4),
  - In the event of pregnancy in a female patient, treatment with the IMP should be discontinued,
  - Follow-up of the pregnancy in a female patient or in a female partner of a male patient is mandatory until the outcome has been determined.

- Symptomatic overdose (serious or nonserious) with IMP/NIMP
  - An overdose (accidental or intentional) with the IMP/NIMP is an event suspected by the Investigator or spontaneously notified by the patient (not based on systematic pills count) within the intended therapeutic interval, adjusted according to the tested drug
    - Infusion: increase of at least 30% of the dose to be administered in the specified duration or if the dose is administered in less than half the recommended duration of administration.
    - Oral: increase of at least 30% of the dose to be taken.

Of note, asymptomatic overdose has to be reported as a standard AE.

- Other project specific AESIs:
  - Cytokine release syndrome.

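### Protocol 9.1.1 prints a DLT list and window that differ from the governing Section 6.2.1, so a few prolonged Grade 2 related reactions could be left uncounted and the patients replaced

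*Protocol*

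**What the plan says.** Protocol 9.1.1 names the endpoint as "Incidence of DLT (as defined in Section 6.2.1) observed during the DLT observation period (6 IMP administrations"), and so points to 6.2.1. It then introduces a separate list: "Potential DLTs are defined as the occurrence of any of the following related to the study therapy". Section 10.5.5 refers to that second list: "Investigational medicinal product related DLTs (as defined in Section 9.1.1) are considered as AESIs".

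The two lists agree on most items. They differ on prolonged reactions:

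- Section 6.2.1, matched by the synopsis: "IMP-related adverse reaction (unless caused by disease progression or an obviously unrelated cause) lasting more than 2 weeks with failure to recover to baseline" or to a low grade. Dosing plays no part.
- Section 9.1.1, under its last item: "IMP-related adverse reaction leading to a delay or omission of more than 2 weeks between 2 planned administrations of SAR440234", because of failure to improve.

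On the window, the synopsis, Sections 6.2.1 and 6.2.2 and SAP Table 2 all give 42 days. Section 9.1.1 gives six administrations. Section 13.3.2 shows that dose level 3 and above receives seven infusions in Cycle 1.

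Section 13.3.2 makes a patient DLT-evaluable with 5 of 6 infusions (dose levels 1 and 2) or 6 of 7 (level 3 and above), or if IMP was stopped because of a DLT. Sections 6.3 and 11.2 replace patients who stop or miss planned dosing for any other reason. SAP Table 6 takes Cycle 1 DLTs from the eCRF DLT page.

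**The concern.** One list tests how long a toxicity lasts. The other tests what it did to dosing. An investigator who works from 9.1.1, as 10.5.5 directs, can leave unreported an event that 6.2.1 calls a DLT.

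The error need not stop at a missed event. A long dose hold in Cycle 1 usually takes the patient below the infusion count for evaluability. Such a patient is kept only if the event is called a DLT. Otherwise the patient leaves both numerator and denominator, and someone else takes the place. In a 3+3 design one such patient can change the decision. DLT incidence is a primary endpoint, and SAP 4.3 keeps the primary safety analyses even though the trial ended early.

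**Working it through.** The plan gives no figure to reproduce here, so the check compares texts and counts dosing patterns.

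**Which events differ.** Nonhematological events of Grade 3 or higher, Grade 3-4 CRS, prolonged Grade 2 CRS and prolonged Grade 4 cytopenias are DLTs in both lists. Grade 1 already counts as recovered. What remains is mainly the nonhematological, non-CRS, IMP-related Grade 2 reaction. Protocol 6.5.5 and Table 9 hold dosing for it until recovery.

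**Held and resumed.** Let x be the days from the last infusion to onset (0 to 6) and D the duration in days (15 to 28). That gives 7 × 14 = 98 combinations. The earliest restart is x + D days after the last infusion, and the next planned infusion was at day 7.

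- Interval reading: 9.1.1 is met if x + D > 14. The smallest value is 0 + 15 = 15, so 0 of 98 escape.
- Delay-past-planned-date reading: 9.1.1 is met if x + D − 7 > 14, that is x + D > 21. Combinations with x + D ≤ 21 escape: 7 for D = 15, 6 for D = 16, and so on to 1 for D = 21. The sum is 7 + 6 + 5 + 4 + 3 + 2 + 1 = 28 of 98, all lasting 15 to 21 days.

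A wider enumeration took onset on Days 1 to 28, duration of at least 15 days and recovery by Day 43, with dosing resumed on the next scheduled day. It has 406 patterns. None escapes on the interval reading; 112 (levels 1-2) and 94 (level 3 and above) escape on the delay reading. All the escaping patterns fail the infusion count. These are counts of patterns, not of patients.

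Example at level 1 or 2: the last infusion is Day 8, and the reaction runs from Day 10 through Day 25 (16 days). Days 15 and 22 are missed and dosing resumes on Day 29. The delay is 29 − 15 = 14 days, which is not more than 14. The interval is 29 − 8 = 21 days. Infusions given are Days 1, 8, 29 and 36, or 4 of 6. Section 6.2.1 calls this a DLT. Section 9.1.1, on the delay reading, does not.

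**Stopped, not resumed.** If the patient leaves IMP before a 2-week delay builds up, there is no later infusion from which to measure one. Section 6.2.1 is still met once the reaction passes 2 weeks.

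**Evaluability.** Infusions fall on Days 1, 8, 15, 22, 29 and 36, plus Day 4 at level 3 and above. Assume missed infusions are not made up within the 42 days, in line with the weekly rule in 6.5.1. A 15-day hold starting on any of Days 1 to 28 then misses at least two infusions, leaving at most 4/6 or 5/7. If the one-day window in 6.5.1 is used, a 15-day reaction starting on Day 1, 8, 15 or 22 (levels 1-2), or on Day 8, 15 or 22 (level 3 and above), still reaches 5/6 or 6/7.

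**Effect of one event under Table 3 and Section 6.3.**

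| Counted under 6.2.1 | Missed under 9.1.1 | If the replacement has no DLT |
|---|---|---|
| 1/3: add 3 patients | 0/2 plus a replacement | 0/3: escalate |
| 2/6 = 0.333: MAD | 1/5 plus a replacement | 1/6 = 0.167: escalate |

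**Window.** At level 3 and above the sixth infusion is Day 29 and the seventh Day 36. If each weekly infusion covers the 7 days from its date, a six-infusion window ends on Day 35, which is 42 − 35 = 7 days short.

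**The case against.** The other side has real weight. Section 9.1.1 itself names 6.2.1 for the endpoint, so the count has a governing definition, and an event that is a DLT under 6.2.1 should not lead to replacement. Section 10.5.5 covers expedited reporting, not evaluability. At the end of Cycle 1 "each patient must be assessed by the Investigator as to whether or not the patient experienced a DLT", whether or not an AESI was sent. Both lists contain the judgement item for any worrying treatment-emergent event, and the Study Committee looks at the whole safety profile. The word between in the 9.1.1 item fits an interval, and on that reading no held-and-resumed case escapes. The six-administration remark is a parenthesis that is right for levels 1 and 2, and nothing says that observation stops at the sixth infusion. A missed Grade 2 event would still be tabulated as a related TEAE.

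This lowers the severity but does not remove the conflict. The end-of-cycle form does not say which list applies. The judgement item needs an opinion about unacceptable risk, which the two-week item in 6.2.1 does not. Section 9.1.1 has the committee review potential DLTs that were reported. The stopped patient is not rescued by the interval reading.

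One further difference matters little: 9.1.1 lacks the 6.2.1 exclusion "AE's related to cytopenias that were present prior to starting SAR440234 or to underlying leukemia will not be considered DLT's". The relatedness condition in 9.1.1 largely covers it, and its absence would lead to over-reporting.

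**Conclusion.** The inconsistency stands, at minor to moderate severity. The window statement is wrong as printed for dose level 3 and above. The two-week item can turn a 6.2.1 DLT into a replaced patient, but only in a narrow set of cases. That conclusion assumes that a site follows 9.1.1 as printed and that missed infusions are not made up. It also assumes either the delay-past-planned-date reading or, for a patient who stops, that the delay must build up while dosing is still intended.

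A reader might infer more than the documents support:

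- That 28 of 98 is a rate. It is a count over equally weighted hypothetical patterns; the documents give no event frequency.
- That DLTs were in fact missed. The eCRF DLT page is not in the documents, so which wording sites used is unknown.
- That low-grade cytopenias lasting over 2 weeks also escape. Section 6.2.1 sets specific hematological thresholds, such as "Grade 4 decreased neutrophils, if not present at baseline and not resolved to baseline value or Grade ≤1 within 14 days", and reading the general item to reach below Grade 4 would make them largely redundant.
- That the definition of an omitted dose in Protocol 13.4.2 settles the stopped-patient case. It is written for exposure in the Expansion Part.

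Because the trial ended early, what remains live is the Cycle 1 DLT listing, the DLT-evaluable population in SAP Table 3, and any MTD or MAD statement built on them.

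**What to change.** Replace the list in 9.1.1 with a cross-reference to 6.2.1. Point 10.5.5 and the eCRF DLT page to 6.2.1 as well. State the window as 42 days and delete the six-administration remark. Add to 6.2.1 that the two-week item applies whether or not dosing is held or stopped.

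Before the DLT listing is finalised, check IMP-related Cycle 1 adverse events lasting more than 14 days in dose-escalation patients against 6.2.1. Include patients replaced as non-evaluable, but not the first 3, whom 13.3.2 excludes. A re-review of daily hematology is not needed.

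The cost is wording in three protocol sections (6.2.1, 9.1.1, 10.5.5) and the eCRF guidance, plus a short check of adverse events in the dose-escalation patients. If the protocol will not be amended again, a sentence in the SAP naming 6.2.1 and 42 days would serve the listing.
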